7.3. Efficacy Assessments

7.3.1. Six-Minute Walk Test

The 6-MWT will be administered by staff trained in the procedure included in the Site Operation Manual. The staff administering the 6-MWT will be different from the Investigator or designee managing the care of the patient.

The 6-MWT will be performed to assess functional exercise capacity and will include pre- and post-walk assessment of O₂ saturation, blood pressure, heart rate, and the Borg scale rating for dyspnea and fatigue. The Screening/Baseline visit assessment will include a practice and an actual 6-MWT at least 1 hour apart and must be done within 28 days prior to randomization. The higher of the two values at Screening/Baseline visit will be used for eligibility purposes. At all other visits, the test should be performed only once at approximately the same time of the day. On dosing days, including Day 0, the 6-MWT should be performed prior to study drug administration. Patients who are hospitalized during the course of the study should wait at least two weeks after hospitalization before completing a 6-MWT assessment.

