9 APPENDICES

Appendix I Details for Co-primary and Secondary Endpoints

A stratified Finkelstein and Schoenfeld Joint Rank Test will be used for the co-primary efficacy endpoint of change from baseline in 6-MWD at 18 months. Pairwise comparison of patients to determine their ranking will be performed using the following steps:

Step 1: Comparison based on time to death

Definition of time to death: Time from date of first dose of study drug to death (months) will be calculated as: (date of death – date of date of first dose of study drug + 1)/30.4. If a patient did not die, time from date of first dose of study drug to death (censoring time) will be calculated as: (date of last study visit –date of first dose of study drug+1)/30.4. Time from date of first dose to death will allow values up to Month 18 analysis visit.

Comparisons can be made if:

- Both patients died and there is no tie in the survival time
- One patient died and the other patient did not die and the time of the death for the patient that died was ≤ the time to death for the patient that did not die (censoring time).

Comparison will be inconclusive if:

- Both patients died and the time to death is a tie
- Both patients were alive
- One patient died and the other patient did not die, and the time of death for the patient was > the time to death of the patient that did not die (censoring time).

Step 2: Comparison based on time to loss of ability to perform 6-MWD

Definition of time to loss of ability to perform 6-MWD:

Loss of ability will be indicated if any of these scenarios occur:

- A patient could not perform the test without an additional walking aids compared to the walking aid used at the screening visits
- A patient could not perform the test without an increase in oxygen flow compared to the oxygen flow used at the screening visits.
- If at a scheduled study visit the patient was unable to perform the test due contraindications (such as: unstable angina within the last month, myocardial infarction within the last month, resting heart rate>120 beats a minute, systolic blood pressure>180 mmHg, diastolic blood pressure>100 mmHg, hospitalization within 2 weeks or other reasons specified (eg, wheelchair)).

Version: 1.0

Alnylam Protocol No. ALN-TTRSC-004

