The time of loss of ability to perform 6-MWD will be based upon the analysis visit. A patient may have more than one onset time for loss of ability to perform 6-MWD during the study. For a patient with more than one scheduled visit where the patient was unable to perform the test, the time of loss will be at the visit where the patient lost and never regained the ability to walk. For a patient not considered to have lost the ability to walk, the time from loss of ability (censoring time) will be calculated as: (date of the latest 6MWD – date of first dose +1)/30.4. Time from first dose to loss of ability will allow values up to Month 18 analysis visit. Note: Any patient that is able to perform the walk at Month 18 visit will be considered a censored patient.

Comparison can be made if:

- Both patients indicated a loss of ability and there is no tie in the time to loss (scheduled visit)
- One patient indicated a loss of ability and the other did not, and the time of the patient who lost the ability to perform the test was \leq the time of the patient who did not lose the ability to perform the test (censoring time).

Comparison will be inconclusive if:

- Both patients indicated a loss of ability and there is a tie in the time to loss (scheduled visit)
- Both patients did not indicate a loss of ability
- One patient indicated a loss of ability and the other patient did not, and the time of the patient who lost the ability to walk > the time of the patient who did not lose the ability to walk (censoring time).

Step 3: Comparison based on change from baseline in 6-MWD

Definition of change from baseline in 6-MWD: Change in 6-MWD (meters) from baseline will be calculated as: (distance walked at post-baseline visits - distance walked at baseline). Baseline will be defined as stated in section 6.1.

To compare change from baseline in 6-MWD (meters) for a pair of patients, the latest common postbaseline study visit that both patients had 6-MWD measurements will be compared. In the event that the change in distance walked from baseline between the pair of patients is identical, a score of 0 (inconclusive) will be assigned to both patients.

Additional details:

- If a patient had > 0 meters for 6-MWD at month 18 and the patient died within month 18 analysis window, then the patient will be considered unable to perform 6-MWD at month 18.

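### In Step 2 of the co-primary 6-MWD test, recovery after a single unable visit is recognised only by a walk at Month 18, so on the literal text a later observed walk can be ignored

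*SAP*

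**What the plan says.** SAP Appendix I, Step 2, sets a broad trigger: "Loss of ability will be indicated if any of these scenarios occur". Besides a new walking aid or more oxygen, it lists: "If at a scheduled study visit the patient was unable to perform the test due contraindications". The examples include reversible states such as a raised heart rate or blood pressure, and "hospitalization within 2 weeks or other reasons specified". Nothing requires the inability to persist.

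The SAP then accepts that ability may be lost more than once. Its dating rule is limited from the first words: "For a patient with more than one scheduled visit where the patient was unable to perform the test". Such a patient's loss is placed "at the visit where the patient lost and never regained the ability to walk". A separate note adds: "Any patient that is able to perform the walk at Month 18 visit will be considered a censored patient". A patient without loss is censored at the date of the latest 6-MWD.

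Protocol 7.3.1 makes temporary inability foreseeable. Patients who have been in hospital "should wait at least two weeks after hospitalization before completing a 6-MWT assessment".

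Protocol 9.2.3.1 (and the synopsis) ranks a pair on death first, then on time until inability. It moves to distance only when neither survival nor duration of walking ability separates the two patients.

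**The concern.** The trigger covers everyone. Recovery is recognised in only two situations: more than one unable visit, or a walk at Month 18. A patient unable at Month 6 because of a recent admission, who walks at Month 12 and withdraws before Month 18, meets neither condition. The Month 6 loss therefore stands although a valid Month 12 walk was recorded.

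Step 2 outranks distance. In every pair not settled on death, this patient loses to any stratum-mate without loss who is censored at or after Month 6, and to any stratum-mate whose loss came later. The Month 12 distance is not used in those pairs. That departs from the Protocol's comparison, because a patient who walked at Month 12 still had the ability then.

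The same gap reaches patients who miss Month 18 without withdrawing, and patients who recover and later die, in pairs where Step 1 is inconclusive.

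**Working it through.** **The plan's own power figure.** SAP 2.3 gives about 90% power for 120 against 60 patients, 0.55 SD, two-sided 0.05, with 13% and 20% deaths.

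- Normal approximation without deaths: 0.55 / √(1/120 + 1/60) = 0.55 / 0.1581 = 3.479; 3.479 − 1.960 = 1.519; power 93.6%. With Wilcoxon efficiency 0.955 it is 92.5%.
- Simulated unstratified Finkelstein-Schoenfeld test with exponential deaths at 13% and 20% and no dropout (3,000 runs): 88.2%.
- 0.55 × 70 m = 38.5 m, and 180 / 0.90 = 200.

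The stated figure is reproduced to within 2 points. It does not depend on the rule at issue.

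**The rule.** SAP 7.6.1.2 places the tests at Months 3, 6, 12 and 18. Let W = walked, U = unable, M = missing after withdrawal. With withdrawal only at the end of a sequence there are 2 + 4 + 8 + 16 = 30 patterns. Applying the never-regained principle to every patient changes four of them:

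| Months 3-6-12-18 | Literal SAP text | One rule for all |
|---|---|---|
| U-W-M-M | loss at Month 3 | censored at Month 6 walk |
| U-W-W-M | loss at Month 3 | censored at Month 12 walk |
| W-U-W-M | loss at Month 6 | censored at Month 12 walk |
| U-U-W-M | no loss time defined | censored at Month 12 walk |

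In the fourth pattern the more-than-one-visit sentence applies, but no visit satisfies it.

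**Size.** The documents give no rate of temporary inability. The simulation assumed a chance of 2%, 5% or 10% at each attended visit, equal in both arms, with 133 and 67 patients, 13% and 20% deaths, a linear course of change and no stratification (2,000 runs). Both rules were run on the same simulated trials. U-U-W-M was treated as censored under both, so only patients unable once count as affected.

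| Dropout | Assumed inability per visit | Patients affected | Power, literal | Power, one rule | Difference (points) |
|---|---|---|---|---|---|
| 10% | 2% | 0.9 | 87.65% | 87.90% | 0.25 |
| 10% | 5% | 2.1 | 83.75% | 84.70% | 0.95 |
| 10% | 10% | 3.8 | 77.90% | 79.15% | 1.25 |
| 20% | 2% | 1.2 | 85.75% | 86.30% | 0.55 |
| 20% | 5% | 2.8 | 81.80% | 82.80% | 1.00 |
| 20% | 10% | 5.1 | 75.40% | 77.90% | 2.50 |

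The fall in power down the table occurs under both rules and comes from the assumed inability itself. Only the last column is due to the wording. A single power figure has a Monte Carlo standard error of about √(0.84 × 0.16 / 2000) = 0.8 points; the differences are paired.

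With unequal assumed rates (10% active, 2% placebo, 10% dropout) power is 58.55% against 62.50%, a difference of 3.95 points. With no treatment effect (5% inability, 10% dropout, 20% deaths in both arms, 3,000 runs) the rejection rate is 5.6% against 5.9%.

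**The case against.** The SAP nowhere states that the patient unable once is a loss after recovering. That follows from the trigger and the absence of an exemption. The authors may have meant recovery to cancel loss for everyone: the Month 18 note applies to any patient, including one unable only once, and the Protocol points the same way. This stands as a statement of likely intent. It does not repair the text, because if the never-regained rule already covered everyone, the Month 18 note would be redundant.

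Several provisions may reduce the number of cases:

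- Assessments have a ±14-day window (Protocol Table 1-1, footnote d), and SAP 6.1 brings unscheduled visits into the analysis windows. A test deferred after a hospital stay may still supply that visit's result.
- The 6-MWT is scheduled at Early Termination, and a late one might map to Month 18. The window definitions are in a separate document.
- Appendix I promises a review of the walk data before lock for unexpected scenarios, but gives no rule for resolving them.
- The step list in SAP 7.6.1.1 and Appendix II (the computational procedure) are missing from the text available here. A clarification there cannot be excluded.

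A reader might also infer that more inability earns a better rank: unable once is a loss, whereas unable twice then walking is censored. The documents do not support this. The twice-unable patient also meets the trigger, and the loss time is undefined; the SAP does not say that this patient is censored.

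**Conclusion.** The point holds as a gap in the ranking rule of a co-primary test. On the literal text, a patient with one unable visit, a later walk and no Month 18 walk is ranked as an early loss, and a twice-unable patient who recovers and withdraws has no defined loss time.

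The likely effect is small: about 1 to 4 of 200 patients and about 0 to 1 point of power at 10% dropout. Every size rests on assumed inability rates, equal across arms, and on an unstratified simulation.

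It would go too far to infer that the rule biases the comparison or inflates type I error. The null simulation shows no material difference between the two rules. The near-4-point power loss needs an imbalance between arms that nothing in the documents supports. The reason to act is that the wording can discard an observed co-primary measurement in a foreseeable case, and correcting it is cheap.

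**What to change.** Replace the more-than-one-visit sentence in SAP Appendix I, Step 2, with one rule for all patients:

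> Loss of ability is dated at the first visit of an unbroken run of unable visits with no later qualifying 6-MWT, whether scheduled, unscheduled or Early Termination. A patient with a later qualifying 6-MWT is not a loss at the earlier visit. A patient with no such run is censored at the latest qualifying 6-MWT.

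Define a qualifying 6-MWT as one performed without the added walking aid or increased oxygen flow that Step 2 already counts as loss. Keep the existing rule for a patient who walks at Month 18 but dies within that analysis window. Check that the step list in SAP 7.6.1.1, Appendix II and the visit-window specification agree with the new wording.

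The cost is a short SAP edit and the matching program change before database lock and unblinding. No new data are needed.

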4.4. Patient Withdrawal

Patients are free to withdraw from the study at any time and for any reason, without penalty to their continuing medical care. There will be no replacements of patients who withdraw from this study. Patients may also be withdrawn if the study is terminated.

If a patient chooses to withdraw from the study, every effort should be made to conduct the Early Termination Visit. When a patient withdraws from the study, the primary reason for discontinuation must be recorded in the appropriate section of the electronic case report form (eCRF) and all efforts will be made to complete and report the observations as thoroughly as possible.

The withdrawn patient will be asked if they are willing to consent to either be contacted by telephone or to allow non-patient contact follow-up (eg, medical record check) 18 months after enrolling onto the study to document their overall health status.

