7.1. Informed Consent

The patient (or the patient's legal guardian) will be given a verbal explanation of the study, including information about the study drug and the study procedures, and will have all questions adequately addressed. The patient (or the patient's legal guardian) must sign and date a consent form that has been approved by the appropriate Institutional Review Board (IRB)/Independent Ethics Committee (IEC) before the Screening/Baseline procedures are initiated. All patients (or their legal guardians) will be given a copy of the signed and dated informed consent form.

If a patient withdraws from the study, in an attempt to minimize the extent of missing data, they will be asked if they would be willing to consent to either be contacted by telephone or to allow non-patient contact follow-up (eg, medical record check) 18 months after enrolling onto the study to document their overall health status.

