2.3 Sample Size and Power

For the 6-MWD primary endpoint, a sample size of 180 with a 2:1 treatment allocation (N=120 on revusiran and N=60 on placebo) has approximately 90% power to detect a treatment difference of 0.55 standard deviations using a Finkelstein and Schoenfeld analysis with a two-sided significance level of 0.05. This assumes that 20% of placebo patients and 13% of revusiran patients will die before the 18 month assessment (ie, hazard ratio = 0.6). Assuming a standard deviation of 70 meters in change from baseline, this would correspond to approximately 90% power to detect a treatment effect of 39 meters in the 6-MWD. Assuming a 10% patient dropout rate, approximately 200 patients will be enrolled in the study. Note that power for the comparison of percent reduction in serum TTR between treatment groups is expected to be >90% for a significance level of 0.05; sustained knockdown of serum TTR levels

>85% has been observed in healthy volunteers and patients receiving revusiran. For this reason, the overall power to establish efficacy is expected to be approximately 90% under the assumptions described above.

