To compare the change in overall summary score from baseline for a pair of patients, the latest common post-baseline study visit that both patients had a non-missing overall summary result will be compared. In the event the change in overall summary score from baseline between a pair of patients is identical, a score of 0 (inconclusive) will be assigned to both patients.

Additional details:

- If a patient did not have any post-baseline information (eg, no information on survival status and no post-baseline data regarding overall summary score), then the patient will be inconclusive for all comparisons.
- If a patient had a missing baseline overall summary score and did not die, then the patient will be inconclusive for all comparisons.

CONFIDENTIAL

Version: 1.0

Alnylam Protocol No. ALN-TTRSC-004

Date of Issue: 21 October 2015

Secondary endpoint: CV Mortality

[figure not shown]
Definition of time to CV mortality: Time from first dose of study drug to CV death (months) will be calculated as: (date of death due to CV – date of first dose of study drug + 1)/30.4. If a patient did not die due to CV, then time from first dose of study drug to CV death (censoring time) will be calculated as: (date of last study visit/date of death not due to CV – date of first dose of study drug+1)/30.4. Time from first dose of study drug to CV mortality will allow values up to Month 18 analysis visit.

[figure not shown]
Secondary endpoint: All-cause Mortality

Definition of time to all-cause mortality: Time from first dose of study drug to all-cause death (months) will be calculated as: (date of death (any reason for death) – date of first dose of study drug + 1)/30.4. If a patient did not die, then time from first dose of study drug to all-cause mortality (censoring time) will be calculated as: (date of last study visit – date of first dose of study drug+1)/30.4. Time from first dose of study drug to all-cause mortality will allow values up to Month 18 analysis visit.

Version: 1.0

Alnylam Protocol No. ALN-TTRSC-004

Version: 1.0

Alnylam Protocol No. ALN-TTRSC-004

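### Survivors are censored at the last study visit while deaths count whenever they occur up to Month 18, so follow-up after withdrawal is used only when it ends in death

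*SAP*

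**What the plan says.** For all-cause mortality, SAP Appendix I counts death from any cause at its date and gives a patient who did not die a time to "all-cause mortality (censoring time) will be calculated as: (date of last study visit", measured from first dose. Step 1 of the joint rank test for 6-MWD uses the same date: "If a patient did not die, time from date of first dose of study drug to death (censoring time) will be calculated as" the interval from first dose to the last study visit. The NYHA and KCCQ tests reuse that step. The composite endpoint and CV mortality censor a living patient at the last study visit but censor a non-CV death at the date of death. All these times are capped at the Month 18 analysis visit. None requires that a death occur while the patient is on study.

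Protocol 4.4 has withdrawn patients asked to consent to a telephone contact or a record check "18 months after enrolling onto the study to document their overall health status". Protocol 7.1 repeats this and gives the reason: "in an attempt to minimize the extent of missing data". Protocol 7.3.12 has mortality and hospitalization events recorded from Day 0 onward, with no end date. Protocol Table 1-1 mentions the contact only in a footnote on withdrawn patients and does not list it as a visit. The SAP assigns it no role.

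**The concern.** The 18-month contact can show that a withdrawn patient is dead or alive. As the SAP is written, a death adds an event and survival adds nothing: the survivor leaves the risk set at the last visit. Time after withdrawal is therefore kept for patients who die and dropped for those who live. This is outcome-dependent censoring, and it inflates estimated mortality in each arm roughly in line with that arm's withdrawals. If withdrawal differs between arms, the comparison shifts too.

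In the joint rank tests, a withdrawn patient known to be alive at 18 months is scored inconclusive on death against anyone who died after that patient's last visit.

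The rule reaches one co-primary endpoint and five of the six secondary endpoints (all but CV hospitalization). The two sensitivity analyses for 6-MWD in SAP 7.6.1.2, a repeated-measures model treating deaths as missing at random and a complete-case ANCOVA, do not test it. SAP 7.6.2.4 and 7.6.2.6 list no sensitivity analysis for the mortality endpoints.

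**Working it through.** **Inputs from SAP 2.3.** "a sample size of 180 with a 2:1 treatment allocation" (120 and 60); "power to detect a treatment difference of 0.55 standard deviations"; deaths by 18 months of 20% on placebo and 13% on revusiran, described as a hazard ratio of 0.6; dropout 10%, about 200 enrolled.

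**The plan's own figures reproduce.**
- Enrolment: 180 / 0.90 = 200.
- Mortality: 1 − 0.80^0.6 = 12.5%, which rounds to the stated 13%.
- Power: simulating the joint rank test without strata (4,000 trials, exponential deaths, a 0.55 SD shift) gives 88.7%, against a stated figure of about 90%.

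**Assumptions that are mine.** Exponential death and withdrawal times; withdrawal unrelated to death; deaths after withdrawal counted; withdrawal rates other than 10% and any split by arm; status known for all withdrawn patients unless stated otherwise.

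**Apparent mortality under the SAP rule.** Let p be true 18-month mortality and w the 18-month withdrawal probability. Set λ = −ln(1−p)/18, ω = −ln(1−w)/18, S(t) = exp(−λt) and G(t) = exp(−ωt). Every death is counted at its date, so the event density is λS(t). The risk set at t contains everyone who will die between t and Month 18, withdrawn or not, plus survivors who have not yet withdrawn: S(t) − S(18) + S(18)G(t). Apparent mortality is 1 − exp(−H), where

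H = ∫₀¹⁸ λS(t) / [S(t) − S(18)(1 − G(t))] dt.

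For p = 0.20 and w = 0.10 the hazard is correct at time 0. At Month 18 it is too high by 0.80 / (0.80 × 0.90) = 1.11. Integrating gives 20.9%. Simulation gives the same figures to within 0.1 point:

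| Withdrawal | True 20% appears as | True 13% appears as |
|---|---|---|
| 5% | 20.4% | 13.3% |
| 10% | 20.9% | 13.6% |
| 20% | 22.0% | 14.4% |
| 30% | 23.2% | 15.3% |

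If status is obtained for only half of those who withdraw, the 10% row becomes 20.5% and 13.3%. If deaths after withdrawal are not counted at all, the estimate is unbiased under these assumptions (20.0%).

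**Pairs in Step 1, at 10% withdrawal.** A between-arm pair loses its comparison on death when one patient dies and the other survives but withdrew before that death. About half of eventual withdrawals precede a given death, so the chance is about 0.05.
- Active death, placebo survivor: 0.13 × 0.80 × 0.05 = 0.0052.
- Placebo death, active survivor: 0.20 × 0.87 × 0.05 = 0.0087.
- Sum: 0.0139, or 1.4% of pairs. With 133 × 67 = 8,911 unstratified pairs, that is about 124.
- With full status, 1 − 0.87 × 0.80 = 30.4% of pairs are decided on death, so about 4.6% of these are lost. Simulation gives 30.6% falling to 29.2%.

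**Treatment comparison.** Dividing events by person-time gives the inflation of each arm's event rate. The true hazard ratio is 0.60, with active mortality 12.5%.
- Equal 10% withdrawal: hazard ratio 0.60 under both rules. Simulated log-rank power with 133 versus 67 patients and deaths of 13% versus 20% is 27.4% under the SAP rule and 27.8% with full status.
- 15% active, 5% placebo: 0.60 × 1.078 / 1.023 = 0.63. Power falls from 26.0% to 21.8%.
- 5% active, 15% placebo: 0.60 × 1.024 / 1.074 = 0.57. With no true effect (20% in both arms), false rejection favouring active is 4.1%, against 3.0% with full status and 2.5% nominal.

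**The case against.** The strongest objection is that the bias rests on an inference. The SAP does not say in words that deaths after withdrawal count. Protocol 8.5 limits adverse event follow-up after early withdrawal, and the per-protocol definition in SAP 5.3 refers to deaths on study. If such deaths were excluded, the bias would vanish under independent withdrawal. This stands as a qualification. Against it, the Appendix I death definition carries no on-study condition, Protocol 7.3.12 sets no end to event recording, and the 18-month contact exists to reduce missing data. Counting the deaths is the natural reading, and the silence itself needs correcting.

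Several stronger inferences are tempting but unsupported:
- *That the trial knows every withdrawn patient's status.* It is sought only from those who consent, and coverage is unknown.
- *That injection site reactions will produce unequal withdrawal.* Protocol 1.3 and 1.6.1 link them to stopping or interrupting drug. Protocol 4.3 encourages patients who stop drug to complete visits through Month 18, and those who do are not censored early. Unequal study withdrawal is possible, but no document shows it.
- *That inconclusive pairs are thrown away.* They pass to the next step. No material effect on the power or type I error of the 6-MWD test has been shown.

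There are also limits of source. Appendix II of the SAP (the joint rank computation) is not in the text available. The SAP cites Protocol 1.0 of October 2014, while the protocol in hand contains January 2016 data, so the contact may postdate the version the SAP was written from. That would explain the gap but would not close it.

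**Conclusion.** The asymmetry is real. Followed as written, the censoring rule uses post-withdrawal follow-up only when it ends in death. This is a wrong rule rather than a missing detail, because the censoring date is stated explicitly.

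Its size is modest. At the planned dropout, mortality is overstated by at most about 0.9 point on placebo and 0.6 on active, and by less as fewer patients consent. The hazard ratio is distorted noticeably only under unequal withdrawal, for which 15% versus 5% is an illustration and not a forecast. The log-rank mortality endpoints are also fourth and last in the testing hierarchy. The rule should be corrected before unblinding, but it does not undermine the trial's main conclusion. All figures depend on deaths after withdrawal being counted and on withdrawal being unrelated to death.

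**What to change.** In SAP Appendix I, for all-cause mortality, CV mortality and Step 1 of every joint rank test, censor survivors at the later of the last study visit and the last date known alive. Include the 18-month telephone or record contact, and cap the time at Month 18. State that deaths after withdrawal are counted up to Month 18, with CV cause decided by the Clinical Adjudication Committee. Add a sensitivity analysis that censors all withdrawn patients at withdrawal, whatever is learned later.

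With full status capture at 10% withdrawal, the re-simulated estimates return to 20.0% and 13.0%.

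The cost is one derived date from follow-up already planned and one extra analysis. There is a small downside: status will be known only for consenting patients, so some imbalance in follow-up can remain if deaths among the others surface by different routes. Deaths found through the contact will also need enough records for adjudication of cause. Protocol 9.2 has the full SAP finalized before database lock, so the change can be made in time.
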